The intervention will be rolled out sequentially during 12 months to 24 hospitals, with six clusters of four geographically close hospitals. Inspections are carried out by six regional teams with members from different County Governors and external clinical experts. Each team conducts four inspections in their region, yielding 24 inspected hospitals. Owing to practical and administrative implications, and general work planning for the involved team members, the four inspections must be clustered together and conducted within a limited time span. Each regional team is assigned a time slot of about seven weeks in which to conduct their inspections; the order of these time slots is randomized (random order generated by computer). Table 1 illustrates the incomplete stepped wedge design used in the study. The design is incomplete in that we do not continuously collect data from all the included sites, rather we collect data at four different time points. The inspections are rolled out successively over one year. On average, there are two inspections each month, though the exact number of inspections each month may vary due to practical work planning for the inspection teams and the involved hospitals.

To answer our research questions, we also need to collect qualitative data. We use focus group interviews to collect qualitative data. The phenomenon that we intend to study is how external inspections affect organizational change processes. Organizational change is dependent on interaction between individuals and groups in the organization.⁴⁷ Focus groups enable interaction between group members during data collection, thus resembling the phenomenon we wish to study. An inspection at a hospital represents one case, and for each case we conduct focus group interviews with the inspection team, leaders in the inspected hospital, and clinicians before and after the inspections.

Table 1. Study design

Year	2015				2016												2017												2018					
Hospital/	S	0	Ν	D	J	F	Μ	Α	М	J	J	Α	S	0	Ν	D	J	F	Μ	Α	Μ	J	J	Α	S	0	Ν	D	J	F	Μ	Α	Μ	J
month																																		
1	P0					FI	P1	SV								P2	FA	FI				Р3	FA											
2	P0						P1	SV								P2	FA					P3	FA											
3	P0							P1	SV								P2	FA					P3	FA										
4	P0							P1	SV								P2	FA					P3	FA										
5	P0							FI	P1	SV								P2	FA	FI				P3	FA									
6	P0								P1	SV								P2	FA					P3	FA									
7	P0									P1	SV								P2	FA					P3	FA								

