8	P0									P1	SV								P2	FA					P3	FA								
9	P0									FI	P1	SV								P2	FA	FI				P3	FA							
10	P0										P1	SV								P2	FA					Р3	FA							
11	P0											P1	SV								P2	FA					P3	FA						
12	P0											P1	SV								P2	FA					P3	FA						
13	P0											FI	P1	SV								P2	FA	FI				P3	FA					
14	P0												P1	SV								P2	FA					P3	FA					
15	P0													P1	SV								P2	FA					P3	FA				
16	P0													P1	SV								P2	FA					P3	FA				
17	P0													FI	P1	SV								P2	FA	FI				P3	FA			
18	P0														P1	SV								P2	FA					P3	FA			
19	P0															P1	SV								P2	FA					P3	FA		
20	P0															P1	SV								P2	FA					P3	FA		
21	P0															FI	P1	SV								P2	FA	FI				P3	FA	
22	P0																P1	SV								P2	FA					P3	FA	
23	P0																	P1	SV								P2	FA					P3	FA
24	P0																	P1	SV								P2	FA					P3	FA

PO: Baseline measurement

SV: Site visit

P1: Measurement before site visit

P2: Measurement 8 months after the site visit

P3: Measurement 14 months after the site visit

FA: Follow-up audit

FI: Focus group interviews

Study population and intervention

Table 2. Key elements of the intervention

Time in months	Activity
1	Inspection team announces inspection and requests the hospital to submit information.
2	Inspection team reviews records of patients with sepsis and collect relevant data for the inspection criteria. Data is collected for two time periods, baseline (September 2015) and right before the site visit. Inspection team reviews information from hospital and prepares for the site visit.
3	Two day site visit at the hospital with interviews of key personnel. At the end of the site visit the inspection team presents the preliminary findings, and the hospital can comment on these preliminary findings.
4-5	The inspection team writes a preliminary report of their findings. The hospital can comment on the report.
6	The inspection team sends the final report to the hospital.
Continuously	The hospital plans and implements improvement measures.
11	Follow-up audit 8 months after the site visit. The inspection team reviews records of patients with sepsis and collect the same data as they did prior to the site visit. Report on findings from audit
17	Follow-up audit 14 months after the site visit. The inspection team reviews records of patients with sepsis and collect the same data as they did prior to the site visit. Report on findings from audit

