If the inspection reveals non-compliant performance, hospital management is responsible for planning and implementing necessary improvements. The inspection teams follow up the hospitals to confirm that necessary changes have been implemented and that the changes in fact improve clinical care. At 8 and 14 months after the inspections, the inspection teams conduct a follow-up audit where they review patient records and collect the same data that they collected prior to the inspection. These data provide insight into how the diagnostic and treatment processes for patients with sepsis are carried out, and is used to judge whether the hospital has managed to improve sepsis detection and treatment. Following the audits at 8 and 14 months, the inspection teams write a short report summarizing the initial findings of the inspection, what the hospital has done to improve their performance and the findings from the audit.

To reduce variation in the delivery of inspections, the Norwegian Board of Health Supervision has developed a common framework standardizing intervention delivery. All audit criteria and the way in which these should be measured are operationalized and described, and a detailed description of how the inspection teams should carry out the inspections is provided. Such a framework can contribute to harmonization of the inspection teams with regard to the way in which key activities are performed.⁵² The inspection teams also receive training and exchange experiences, to harmonize the way in which they deliver the intervention.

Data collection

Quantitative data

Figure 2 outlines the clusters and the data collection. For each inspection, we collect data at four different time points, referred to as P0, P1, P2, and P3. P0 is the baseline measurement for all hospitals before the Norwegian Board of Health Supervision announced the inspection campaign. The campaign is part of the regular planned inspection activities. These activities are transparent for the hospitals and are announced in advance, in this particular case six months before the first inspection. Due to practical reasons, the inspection teams collect data for P0 and P1 at the same time right before the inspection. Data for P0 are thus collected retrospectively, but it is pre-defined that the patients that will be included are the last patients with suspected sepsis that were admitted prior to October 1st 2015.

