Descriptive statistics will be used to quantify sample characteristics. All analysis will use patient-level data, collected at four periods for different patients for 24 hospitals – two collections during the control period and two collections during the intervention period for each hospital. In order to compare the various process and outcome measurements (dependent variables) between the intervention and control periods (independent variable), we will use logistic regression models for binary measurements and linear regression models for continuous measurements. The choices of regression methods for the various measurements are outlined in table 3. As recommended in literature, ^{63 64} all models will include time as a covariate to adjust for potential secular changes in the

process and outcome measurements during the study period. The underlying form of time will be included in the models as a linear term, polynomial term, or cubic spline term, as appropriate.

Norway is divided into 18 counties in addition to its capital city, and there are acute hospitals that treat patients with sepsis in all counties. The population density varies between the counties. The smallest acute hospitals serve a population of about 50 000, while the largest serve a population of about 500 000. The sizes of the ICU units and the number of patients with sepsis treated during a year will therefore differ between the included hospitals. This is a national inspection campaign, and hospital in all counties will be inspected. As patients are sampled from different hospitals, a between-hospital variation in measurements is likely, introducing correlated data within the hospitals. To account for this intra-cluster correlation, we will use generalized estimating equations methodology,⁶⁵ specifying an exchangeable working correlation structure, i.e., any two patients are equally correlated within hospitals regardless of time and intervention and control periods. However, as this assumption might not hold for all hospitals, a method for obtaining cluster-robust standard errors of model parameters will be applied.⁶⁶ Finally, as our repeated sampling of patients with sepsis may not be entirely representative of the total population, difference in certain patient characteristics, including age and sex, between comparison periods might arise. In that case, the abovementioned models will also include such covariates for obtaining correct model means.

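### The baseline is sampled at one time of year and no seasonal term is planned, so the simpler permitted time forms would let part of any annual cycle into the inspection effect

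*Combined protocol and SAP*

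**What the plan says.** The section on quantitative data collection defines P0 in all 24 hospitals as "the last patients with suspected sepsis that were admitted prior to October 1st 2015". Table 2 gives the same timing: "Data is collected for two time periods, baseline (September 2015) and right before the site visit". P0 is therefore a count of records working back from a fixed date.

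The other samples move with the roll-out: "The inspections are rolled out successively over one year". The key to Table 1 adds "P2: Measurement 8 months after the site visit" and "P3: Measurement 14 months after the site visit". Read off Table 1, P1 runs from March 2016 to February 2017, P2 from December 2016 to November 2017, and P3 from June 2017 to May 2018, with two hospitals per calendar month in each.

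The section on statistical analysis compares "two collections during the control period and two collections during the intervention period for each hospital". It says that "all models will include time as a covariate to adjust for potential secular changes in the" measurements, entered as a "linear term, polynomial term, or cubic spline term, as appropriate". It gives no polynomial degree, number of knots or rule for choosing. Season is not mentioned there, nor in the section on strengths, limitations and biases, which argues that confounders and case mix should not differ before and after inspection.

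**The concern.** Half of the control-period data come from one point in the annual cycle. The other three samples are balanced over the year, and P2 and P3 are six months apart within each hospital, so an annual cycle cancels in their simple mean. If mortality or emergency-department timeliness varies with season, the before and after periods differ for a reason unrelated to inspection.

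A time covariate chosen to follow a slow trend need not correct this. A straight line cannot bend with the year, and a cubic or small spline can follow part of the cycle and redistribute it among the samples. The 30-day mortality analysis is the most exposed, because its target difference is only 3.5 points (15% to 11.5%).

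**Working it through.** **Inputs from the plan.** 24 hospitals; four samples each; 33 records per sample for process measures and 60 for mortality; intra-cluster correlation 0.05; exchangeable correlation within hospital; targets 50% to 65% (antibiotics) and 15% to 11.5% (mortality). Counting months from September 2015: P0 = 0, P1 = 6 to 17, P2 = P1 + 9, P3 = P1 + 15.

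**Plan's own figures.** 24 x 4 x 33 = 3168 and 24 x 4 x 60 = 5760 agree. The plan has no figure on season to reproduce. Its 80% power for mortality does not reproduce on this layout (49% with linear time). The step layout used for the power calculation is not given; that is a separate matter and nothing below rests on it.

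**Assumption.** A season of the form A cos(2π(t - φ)/12), where A is the mean-to-peak amplitude and φ the peak month. Neither is in the documents, so results are multiples of A at every phase.

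**Hand check, no time term.** The effect is (P2 + P3)/2 - (P0 + P1)/2. P1, P2 and P3 each average to zero over 12 equally spaced months, so the bias is -0.5 A cos(2πφ/12), at most 0.50A, all from P0.

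**With a time term.** The effect estimate is w'y, where w is the treatment row of (D'V⁻¹D)⁻¹D'V⁻¹. D holds the P2/P3 indicator, an intercept and the time terms. V has, within hospital, σ² x 0.05 off the diagonal and σ² x (0.05 + 0.95/m) on it. For mortality σ² = (0.15 x 0.85 + 0.115 x 0.885)/2 = 0.1146. The bias is the sum of w times the cosine. Largest absolute bias over all phases, m = 60:

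| Time term | Largest bias / A |
|---|---|
| None | 0.50 |
| Linear | 0.56 |
| Quadratic | 0.44 |
| Cubic | 1.01 |
| Restricted cubic spline, 3 / 4 / 5 quantile knots | about 0.4 / 0.8 / 0.9 |
| Restricted cubic spline, 6 / 8 / 10 equally spaced knots | 0.13 / 0.11 / 0.02 |

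At m = 33 the linear, quadratic and cubic values are 0.54, 0.43 and 1.02, and a degree-8 polynomial gives 0.04.

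**Sign by peak month** (negative means inspection appears to lower the rate). January: linear -0.36, cubic -0.11. February: linear -0.53, cubic +0.40. The cubic maximum arises with an April or October peak.

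**Source of the bias** (September peak, m = 33). Linear: P0 contributes 0.558 of a total of 0.527. Cubic: P0 contributes 0.036, P1 0.116, P2 -0.571 and P3 -0.395, total -0.814. P0 dominates with linear time; P1 to P3 dominate with cubic time.

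**In points, mortality, A assumed 1 to 2.** Linear: 0.56 x 1 = 0.6 to 0.56 x 2 = 1.1. Cubic: 1.01 x 1 = 1.0 to 1.01 x 2 = 2.0. Worst-phase type I error at a nominal 5% is 6% to 9% (linear) and about 7% to 12% (cubic). At A = 3 it would be 14% and 21%.

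**In points, antibiotics, A assumed 1 to 2.** Linear: 0.54 x 1 = 0.5 to 0.54 x 2 = 1.1. Cubic: 1.02 x 1 = 1.0 to 1.02 x 2 = 2.0. The target is 15. At A = 5 the worst cases are 2.7 and 5.1.

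**Check on the planned model.** In 120 simulated logistic GEE fits with no effect and a logit amplitude of 0.2, at the worst phase for linear time, bias per unit amplitude was +0.48 (linear), -0.73 (cubic), -0.19 (6-knot spline) and -0.03 (linear plus sine/cosine pair, within Monte Carlo error).

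**The case against.** The strongest reply is that the plan already permits a suitable model. It caps neither degree nor knots, and a spline with six or more well-spaced knots, or a high-degree polynomial, lets through little of an annual cycle. This stands against the reading that no permitted time form can handle season. It does not close the point, because nothing in the plan requires such a form, and splines with 3 to 5 knots still let through 0.4 to 0.9.

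The size is also assumed. A reader might infer that season does bias the result, or that a winter mortality peak will make inspection look protective. The documents support neither: they give no amplitude or phase, and for a February peak linear and cubic time point in opposite directions. The cubic worst case should not be attached to a winter peak.

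A reader might also take P0 to be late September only. The plan fixes the end date and samples by count, so small hospitals may reach further back. Averaging P0 over July to September hardly changes the result (linear 0.55, cubic 1.04).

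Finally, adjustment for age, sex and organ dysfunction could remove seasonal differences that run through those variables. That is fair, but the adjustment for age and sex is conditional on observed differences, and none of the three represents season itself.

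**Conclusion.** The point holds as a gap in pre-specification. No seasonal term is planned, the form of time is left open, and the simpler permitted forms pass a worst-phase share of about 0.4 to 1.0 of an annual amplitude into the inspection effect, with a sign that depends on the form chosen. It matters mainly for 30-day mortality: on an assumed amplitude of 1 to 2 points, up to about a third of the 3.5-point target with linear time (1.1/3.5 = 0.31) and somewhat over half with cubic time (2.0/3.5 = 0.57). On the same assumption it is minor for antibiotics within one hour.

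The multiples rest on the Table 1 months being kept, an intra-cluster correlation of 0.05 and a sinusoidal season. The figures in points rest also on the assumed amplitude. The fixed baseline is not the general cause: it is the whole source without a time term and the main one with linear time, but not with a cubic or a 4-knot spline.

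**What to change.** Pre-specify one annual pair, sin(2πt/12) and cos(2πt/12) with t the admission date in months, added to the trend term in every model. State that time is continuous and taken from each patient's admission date; the plan says only that time is a covariate. Fix the trend form, including any degree or knots, before the outcome data are examined. Admission dates are needed for the sampling and for 30-day mortality, so no new data should be required.

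Cost: two model terms. The mortality standard error rises from 0.0181 to 0.0185 with linear time (about 2%) and from 0.0254 to 0.0268 with cubic time (about 6%). On this layout with linear time, power for 15 points on antibiotics goes from 99.0% to 98.7%, and power for 3.5 points on mortality from 49% to 47%. The alternatives cost more: a 6-knot spline gives a mortality standard error of 0.0275, and full calendar-month effects 0.0311.

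The pair removes a sinusoidal annual cycle exactly in the linear calculation. A sharper seasonal peak may leave a residual.

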Data for P0 are collected from the time period right before the inspection campaign was announced. All hospitals know that they can be inspected. By collecting data before the campaign was announced we can track changes throughout the inspection cycle and assess to what extent changes are implemented before the inspections are undertaken. P1 is the pre-inspection measurement, and P2 and P3 are post-inspection measurements. The regional inspection teams collect data during the inspection and audits conducted 8 (P2) and 14 months (P3) following the initial inspection. These data serve two purposes. They are used to guide the judgments on whether the inspected hospitals comply with the requirements, and to evaluate how inspections affect the clinical processes involved in diagnosing and treating sepsis.

Figure 2. Illustration of clusters and data collection

We use a two-step approach to identify eligible patients who might have sepsis upon arrival at the hospital. First, a record search of the National Patient Register (NPR) is carried out, using diagnostic codes for infections and sepsis. The NPR is a national common register of all patients and the treatment they have received in Norwegian hospitals. This record search will produce a list of patients with an identification number that will enable the inspection teams to access the corresponding patient records at inspected hospitals. Second, the inspection teams assess the individual patient records for eligibility. The inclusion criteria are clinically suspected infection and at least two systemic inflammatory response syndrome (SIRS) events, excluding elevated leukocytes.⁵³ The inspection teams extract data from the included patient records.

Based on the literature, previous research, and discussion with clinical experts, we identified relevant effect measures that reflect how hospitals handle patients admitted to the hospital with suspected sepsis.^{28 54} These indicators are displayed in box 3. In addition, data are collected for the following control variables: patient sex and age, sepsis with organ dysfunction, and hospital size.

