We use 30-day mortality rate as our key outcome measure, defined as the ratio of patients with sepsis who are dead within 30 days of hospital admittance. Mortality measures based on in-hospital deaths alone, can be misleading as indicators of hospital performance.⁵⁵ Our measure also includes out of-hospital deaths. Using the unique personal identification number provided to all citizens of Norway, we are able to link the patient record data with data from the National Registry to calculate the 30-day mortality rate. 30-day mortality rate is an established, national quality indicator for Norwegian hospitals,⁵⁶ and this indicator has been shown to have better validity as a hospital performance measure than in-hospital mortality for selected medical conditions.⁵⁷ 30-day mortality rate has also previously been used to assess effects of measures to improve care for patients with sepsis.⁵⁸

Process measures

- 1. Percentage of patients who have been triaged within 15 minutes of arrival in the emergency room
- 2. Percentage of patients who have been assessed by a medical doctor within the time frame set during triage
- 3. Percentage of patients in which vital signs have been evaluated within 30 minutes
- 4. Percentage of patients in which blood lactate has been measured within 30 minutes
- 5. Percentage of patients from which supplementary blood samples have been taken within 30 minutes
- 6. Percentage of patients from which a blood culture is taken prior to administration of antibiotics
- 7. Percentage of patients in which adequate supplementary investigation to detect locus of infection has been undertaken within 24 hours
- 8. Percentage of patients who have received antibiotics treatment within 1 hour of arrival in the emergency room
- 9. Percentage of patients who have received intravenous fluids within 30 minutes
- 10. Percentage of patients who have received oxygen therapy within 30 minutes
- 11. Percentage of patients for whom an adequate surveillance regime has been established
- 12. Percentage of patients who have been adequately discharged from the emergency room for further treatment in the hospital (written statement indicating patient status, treatment, and further actions)

Outcome measures

- 1. Hospital length of stay
- 2. 30-day mortality rate

Box 3: Effect measures

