We consider the percentage of patients with organ dysfunction who have received antibiotic treatment within one hour as the key measure, because it is associated with our outcome measure, 30-day mortality rate.^{27 28} Furthermore, we suggest that early triage and early assessment by medical doctor are key activities to secure timely treatment with antibiotics, and that the corresponding process measures consequently are important too.

The power calculations were performed using the *steppedwedge* function in Stata/IC version 14.0 (StataCorp LLC, College Station, TX, USA) software for Windows, developed by Hemming and Girling.⁵⁹ The statistical power in a stepped wedge design depends on the total number of intervention sites, the total number of data collection points for each intervention site, the number of patient records included at each data collection point, the correlation between clustered observations on the same hospital (intra-cluster correlation), and the implementation period.⁴⁵ We based our calculations on 24 intervention sites, 4 data collection points, and 33 patient records per

collection point at each intervention site. As the intra-cluster correlation may vary between samples and between process and outcome measurements, it is not straightforward to specify an intracluster correlation in advanced. In addition, we could not find any estimated intra-cluster correlation in previous trials of patients with sepsis. Consequently, we chose an intra-cluster correlation of 0.05, which is in line with that estimated for several patient outcomes in a cluster randomized trials of heart failure patients.⁶⁰ Type I and II errors were assumed to be 0.05 and 0.20, respectively.

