Because assessment of patient records must be done manually, data collection is resource demanding. Thus, we must balance the design and power of the study against the available resources, a manageable amount of data collection, and likely detectable changes in the key effect measures. For the process data, we have powered the study according to the key clinical process indicator, antibiotic treatment within 1 hour of arrival at the hospital. To detect an absolute improvement of 15 percentage points, e.g., from 50% to 65% of patients receive antibiotic treatment within 1 hour of 2376 patient records. We intend to include n=3168 patients (24 hospitals × 4 time points × 33 patients); we assert that this sample is large enough to examine the other relevant process indicators described in box 3.

To reach sufficient statistical power to detect a significant change in patient outcome measures, such as 30-day mortality rate, we need to include more than the 33 patients that we include to detect changes in process measures per each time point. We have powered the study to detect a reduction from 15% to 11.5% in the mortality rate by including 60 patients for each hospital at each time point. The total intended number of included patients for outcome measures is n = 5760 patients (24 hospitals × 4 time points × 60 patients).

Qualitative data

We conduct focus group interviews based on an interview guide. We developed the interview guide based on theory about practices involved in implementing organizational change⁶¹ along with our model for how inspections can contribute to improving quality of care by affecting organizational change activities and ideas.³⁹ The key research questions that will be further explored in the qualitative study are displayed in box 4.

- How do inspection teams plan, conduct, follow up, and finalize the inspections?
- How do the inspected organizations prepare for inspections?
- Do inspections contribute to creating awareness about current performance and possible performance gaps in the clinical system for delivering care to patients with sepsis?
- Do inspections contribute to engaging leaders and clinicians in improvement of their work?
- Do hospitals initiate improvement activities aimed at enhancing the quality of sepsis care prior to inspections?
- Do inspections affect organizational ideas, e.g., understanding of the clinical system and

commitment to change?

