Indicator	Dependent variable	Туре	GEE model ¹
Process	Triage within 15 minutes	Binary	Logistic regression
Process	Timely assessment by physician	Binary	Logistic regression
Process	Vital signs evaluated within 30 minutes	Binary	Logistic regression
Process	Blood lactate measured within 30 minutes	Binary	Logistic regression
Process	Supplementing blood samples within 30 minutes	Binary	Logistic regression
Process	Blood culture taken before antibiotics	Binary	Logistic regression
Process	Adequate supplementing investigation within 24 hours	Binary	Logistic regression
Process	Antibiotic treatment within 1 hour	Binary	Logistic regression
Process	Intravenous fluid within 30 minutes	Binary	Logistic regression
Process	Oxygen therapy within 30 minutes	Binary	Logistic regression
Process	Adequate surveillance regime established	Binary	Logistic regression
Process	Adequate discharge from emergency room	Binary	Logistic regression
Outcome	30-day mortality	Binary	Logistic regression
Outcome	Length of stay	Continuous ²	Linear regression

Table 3. Outline of regression models for the various process and outcome measurements

¹ Regression models with generalized estimating methodology (GEE).

² Transformed if skewed distribution.

Qualitative analysis

The focus group interviews will be taped and transcribed. We will perform a thematic content analysis of the data guided by theory and the data themselves.⁶⁷ The quantitative data will indicate whether the clinical processes have improved. The focus for the analysis of the qualitative data is to understand more about why and how the clinical processes for detecting and treating sepsis have been changed or not changed.

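### The key process measure is defined in patients with organ dysfunction, but its listing, its model row and its sample size carry no such restriction

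*Combined protocol and SAP*

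**What the plan says.** All places are in the combined protocol and SAP.

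- **Data collection, Quantitative data, text after Box 3:** "We consider the percentage of patients with organ dysfunction who have received antibiotic treatment within one hour as the key measure". The reason given is its association with 30-day mortality.
- **Box 1:** the 60-minute antibiotic criterion is stated for patients with organ dysfunction. For patients without it, the box sets no fixed limit.
- **Box 3, item 8:** "Percentage of patients who have received antibiotics treatment within 1 hour of arrival in the emergency room". No subgroup is named.
- **Table 3:** the row reads "Antibiotic treatment within 1 hour", with a logistic GEE model and no population.
- **Sample size paragraph:** "we have powered the study according to the key clinical process indicator, antibiotic treatment within 1 hour of arrival at the hospital". The example is a rise from 50% to 65%, and the intended sample is given as "We intend to include n=3168 patients (24 hospitals × 4 time points × 33 patients". The same records are to serve the other Box 3 indicators.
- **Inclusion:** "The inclusion criteria are clinically suspected infection and at least two systemic inflammatory response syndrome (SIRS) events, excluding elevated leukocytes". Organ dysfunction is not required. It is listed as a control variable, and the section on strengths, limitations and biases says that it can be adjusted for.

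**The concern.** The result that the plan itself calls key has two possible denominators. An analyst who follows the sentence after Box 3 would analyse patients with organ dysfunction. One who follows Box 3 and Table 3 would analyse every included patient. Both would be following the document, and they could report different percentages and different intervention effects. Adjusting for organ dysfunction does not resolve this, because a covariate does not restrict a denominator.

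The sample size is tied to the same question. If the key measure is limited to patients with organ dysfunction, only part of the 33 records per hospital and time point enters the analysis, and the stated size is not a size for that measure. If all patients are meant, the sentence defining the key measure is wrong as written.

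**Working it through.** **1. What the stated totals count.** 24 hospitals × 4 time points × 33 records = 3168, the intended sample. The other total stands in a sentence that appears to have lost words: "of patients receive antibiotic treatment within 1 hour of 2376 patient records". Arithmetically, 2376 = 24 × 3 × 33. A layout of three steps of eight hospitals, four periods, categorical time and one implementation period per hospital left out gives this total, with 80.8-84.4% power for 50% to 65% at an intra-cluster correlation (ICC) of 0.05. That layout is inferred; the plan does not state it and it differs from Table 1. Either way, both totals use 33 included records per cell, with no factor for organ dysfunction.

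**2. What remains if the measure is restricted.** Let f be the share of included patients with organ dysfunction. The documents do not give f, so a range is assumed.

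- Records per cell = 33 × f: 16.5 at f = 0.5; 9.9 at f = 0.3.
- Total = 3168 × f: 1584 at f = 0.5; about 950 at f = 0.3.

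**3. Power for the restricted measure.**

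Inputs from the plan: 24 hospitals, ICC 0.05, type I error 0.05 (taken as two-sided), 50% to 65%. Timing from Table 1, in months from September 2015: P0 at 0, P1 at 6 to 17 with two hospitals per month, P2 = P1 + 9, P3 = P1 + 15.

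Assumptions: the 50% to 65% example applies to patients with organ dysfunction; the hospital correlation is exchangeable; the effect is approximated on the risk-difference scale. The binary variance is 0.239, 0.244 or 0.25, each taken as total or as residual variance, which produces the ranges.

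For hospital i, V_i = (σ²/m)I + τ²J with m = 33f. SE is the square root of the treatment element of (Σ D_i′V_i⁻¹D_i)⁻¹, where D_i holds an intercept, the time terms and the intervention indicator. Then power = Φ(0.15/SE − 1.96), and the difference detectable at 80% power = (1.96 + 0.84) × SE.

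| f | Power, linear time | Power, quadratic time | Detectable difference, linear (points) | Detectable difference, quadratic (points) |
|---|---|---|---|---|
| 1 | 98-99% | 97-98% | – | – |
| 0.5 | 83-87% | 80-84% | 13.7-14.4 | 14.3-15.0 |
| 0.3 | 63-67% | 60-64% | 17.5-18.4 | 18.1-19.0 |

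Arithmetic check at f = 0.5, linear time: SE = 13.7/2.80 = 4.89 points, and Φ(15/4.89 − 1.96) = Φ(1.11), about 87%. At the other end, SE = 14.4/2.80 = 5.14, and Φ(15/5.14 − 1.96) = Φ(0.96), about 83%.

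Under this schedule, 80% power is kept if f is at least 0.42-0.46 with linear time, or 0.45-0.50 with quadratic time.

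**The case against.** **The text can be read as consistent.** The sample size paragraph refers to the key indicator shortly after the key measure has been defined, so it may simply refer back. Box 1 also ties the time limit to organ dysfunction. On that reading, Box 3 and Table 3 are short labels that dropped a qualifier. This is plausible, but it does not repair the sizing: the 33 records per cell are still all included patients, and the same records are meant for the unrestricted indicators.

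**The denominator may be defined elsewhere.** The plan mentions a framework that operationalises the audit criteria and details the data to be collected (Study population and intervention; Data monitoring). It is not part of the document and may settle the point. The claim is therefore limited to the protocol/SAP, which should still state the denominator of its own key result.

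**The consequence is limited.** The plan calls the measure key, not primary, lists twelve process measures and sets no testing order. Both versions can be produced from the data collected. This makes the discrepancy easy to repair but does not remove it.

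**Stronger readings that the documents do not support.**

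- A reader might infer that the study is underpowered for its key measure. The documents give no f, and at f = 0.5 power stays at about 80% or above with linear or quadratic time. With cubic time it is 57-61%, but cubic time already brings it down to 84-87% at f = 1. Part of that loss therefore comes from the choice of time term, which the plan leaves open ("included in the models as a linear term, polynomial term, or cubic spline term, as appropriate") and which is a separate matter. The inferred 2376 layout gives 55-59% at f = 0.5, but it is not in the plan and should carry no weight.
- A reader might take 2376/3168 = 0.75 as an expected share with organ dysfunction. No text says so.
- A reader might take the limitations section, which says that the process measures remain relevant for the whole included population, as fixing the denominator. That passage is about the new sepsis definition and does not define the key measure.

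**Conclusion.** The inconsistency stands with high confidence, because it rests on the wording alone. The key measure is defined in patients with organ dysfunction; Box 3 item 8, Table 3 and the sample size paragraph do not carry the restriction, and nothing in the protocol/SAP reconciles them. It also follows that 33 per cell, 2376 and 3168 are not sample sizes for the measure as defined, unless every included patient had organ dysfunction.

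The effect on power is conditional. It depends on f, on whether the 50% to 65% example holds in these patients, and on the time term; the figures of 80-87% and 60-67% at f = 0.5 and 0.3 hold only under the assumptions listed. No shortfall is demonstrated, and the documents do not show which denominator was intended. The point should be fixed, but it does not invalidate the design.

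**What to change.** Reconcile the sentence after Box 3, Box 3 item 8, the Table 3 row and the sample size paragraph so that one denominator is named for the key measure. Date that choice. Report the other population as a named secondary measure with its confidence interval, using the organ dysfunction flag already collected.

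- **If the organ dysfunction definition stands:** restrict that row of Box 3 and Table 3 accordingly. State in the sample size paragraph that the sizing covers all included records, and give the detectable difference for 33 × f records per cell over a stated range of f.
- **If all included patients are meant:** correct the sentence that defines the key measure, and name the organ dysfunction subset as the secondary version.

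The cost is wording in four places and, in the first case, a short table; no further records are needed. There are two drawbacks. The stated power for a restricted key measure becomes less favourable. The choice may also be made after data were available, since the document is dated November 2021 and the Table 1 schedule ends in June 2018. Dating the choice and reporting both versions limits that second problem but does not remove it.
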